12.4 PARTICIPANT AND DATA CONFIDENTIALITY

Subject confidentiality is held in strict trust by the participating investigators, their staff, the Sponsor, and their agents. This confidentiality is extended to cover testing of biological samples in addition to the clinical information relating to subjects. Therefore, the study protocol, documentation, data, and all other information generated will be held in strict confidence. No information concerning the study or data will be released to any unauthorized third party without prior written approval of the Sponsor.

The study monitor, other authorized representatives of the Sponsor, representatives of the IRB, or government regulatory agencies may inspect documents and records required to be maintained by the investigator, including but not limited to, medical records (office, clinic, or hospital) and pharmacy records for the subjects in this study. The clinical study site will permit access to such records.

The study subject's contact information will be securely stored at each clinical site for internal use during the study. At the end of the study, all records will continue to be kept in a secure location for as long a period as dictated by local IRB, Institutional regulations or Clinical Trial Agreement, whichever is longest. Subject data that is transmitted to the Sponsor, CRO, and/or IRB will not include contact or identifying information. Rather, individual subjects and their research data will be identified by a unique study number. This unique study number should be recorded on non-local lab samples, requisitions, and any documents submitted to the CRO, Sponsor, and/or IRB. The study data entry and study management systems used by clinical sites and by research staff will be secured and password protected.

12.5 FUTURE USE OF STORED SPECIMENS

With the subject's approval and as approved by IRBs, biological samples may be stored at Alkahest, or designee, for future use. These samples could be used for future research designed to improve methods for diagnosis, prevention, and/or treatment. Alkahest will also be provided with a code-link that will allow linking the biological specimens with the specific data from each subject, maintaining blinding of the identity of the study subject. Subjects may choose whether the Sponsor can store and use samples for further research.

During the conduct of the study, an individual subject can choose to withdraw consent to have biological specimens stored for future research. However, withdrawal of consent for biospecimen storage will not be possible after the study is completed.

When the study is completed, access to study data and/or samples will be managed by Alkahest. In the event Alkahest transfers ownership to another commercial Sponsor, ownership of the samples may be transferred as well.

13 DATA HANDLING AND RECORD KEEPING

13.1 DATA COLLECTION AND MANAGEMENT RESPONSIBILITIES

Data collection is the responsibility of the clinical trial staff at the site under the supervision of the site investigator. The investigator is responsible for ensuring the accuracy, completeness, and timeliness of the data reported.

Source documents provide evidence for the existence of the subject and substantiate the integrity of the data collected. Source documents are filed at the investigator's site. Data entered in the CRFs that are transcribed from

source documents must be consistent with the source documents or the discrepancies must be explained. All source documents should be completed in a neat, legible manner to ensure accurate interpretation of data. Black or blue ink is required to ensure clarity of reproduced copies. When making changes or corrections, cross out the original entry with a single line, and initial and date the change. DO NOT ERASE, OVERWRITE, OR USE CORRECTION FLUID OR TAPE ON THE ORIGINAL. The investigator may need to request previous medical records or transfer records, depending on the trial; also, current medical records must be available.

The CRF must be completed in a timely manner. The investigator will review and approve the CRF for each study subject after all data have been entered, the CRFs have been source document verified, and all queries have been resolved. This also applies to records for those subjects who fail to complete the study. If a subject withdraws from the study, the reason must be noted on the CRF. If a subject is withdrawn from the study because of an AE, thorough efforts should be made to clearly document the outcome.

13.1.1 INVESTIGATOR RESPONSIBILITIES

The investigator will comply with the protocol (which has been approved/given favorable opinion by an IRB), ICH GCP, and applicable regulatory requirements. The investigator is ultimately responsible for the conduct of all aspects of the study at the study site and verifies by signature the integrity of all data transmitted to the Sponsor. The term “investigator” as used in this protocol as well as in other study documents, refers to the investigator or authorized study personnel that the investigator has designated to perform certain duties. Sub-investigators or other authorized study personnel are eligible to sign for the investigator, except where the investigator’s signature is specifically required.

13.1.1.1 Reporting Responsibilities

Investigators are required to:

- Submit AEs/ADEs/SAEs/SADEs/UADEs to the study Sponsor or designee, as per the reporting requirements outlined in [Section 8.4](#).
- Submit to their IRB a report of any UADEs, or events of subject death, occurring during an investigation as soon as possible but in no event later than 10 working days after the investigator first learns of the event.
- Notify the study Sponsor of withdrawal of IRB approval or other action on the part of the IRB that affects the study as soon as possible but in no event later than 5 working days.
- Notify the Sponsor, Monitor, and IRB of study progress at regular intervals but in no event less often than yearly.
- Notify the Sponsor/IRB of any significant deviations from the investigational plan for emergency purposes, as soon as possible but in no event later than 5 working days after deviation occurs to protect the life or physical well-being of a subject in an emergency.
 - For non-emergency purposes, obtain prior approval by Sponsor and, if deviation may affect scientific soundness of the trial or the rights, safety, or welfare of subject, also obtain approval by the IRB and FDA as an Investigational Device Exemption (IDE) supplement.
- Notify the Sponsor and IRB if a subject is treated with an investigational device without first obtaining informed consent, within 5 working days of use of the investigational device.
- Notify the Sponsor and IRB with a final study report within 3 months after termination or completion of study or termination of site’s participation.

13.1.2 STUDY FILES

Investigators are required to maintain on file the following accurate, complete, and current records relating to this study:

- All correspondence relating to the study with another investigator, an IRB involved in the study, Alkahest, Inc., a monitor, or FDA, including required reports.
- Records of receipt, use, or disposition of a device.
- All clinical forms and documentation, including:
 - Records of each subject's case history and exposure to the device.
 - A copy of the signed subject consent form.
 - Date and time of exposure to the investigational device.
 - All procedure and follow-up report forms, including supporting documents.
 - Records of any adverse event or device effect, including supporting documentation.
 - Records pertaining to subject deaths during the study.
 - The study protocol/amendments including documentation and rationale for any deviations from the clinical protocol.
 - Any other records required by Alkahest, Inc. or FDA.

The investigator's study file will contain all of these documents, as well as staff curriculum vitae and authorization forms, and other appropriate documents and study-specific manuals (e.g., Device Procedures Manual).

13.2 STUDY RECORDS RETENTION

Per 21 CFR 812.140(d), an investigator or Sponsor shall maintain the records required by this subpart during the investigation and for a period of 2 years after the latter of the following 2 dates: the date on which the investigation is terminated or completed, or the date that the records are no longer required for purposes of supporting a premarket approval application, a notice of completion of a product development protocol, a humanitarian device exemption application, a premarket notification submission, or a request for De Novo classification.

Before the investigator destroys any material related to the clinical study, he/she must obtain approval in writing from the Sponsor.

The investigator should keep a file where the full name and address of the subject and all signed informed consents are included for at least 15 years after completion of the trial. Any original study-related information that permits verification of inclusion and exclusion criteria, including clinical history, a copy of all data collection logs, and documents on the use of the study device, must be stored for as long a time period as permitted by the center.

Should the investigator wish to move study records to another location, arrangements must be made to store these in sealed containers so that they can be returned sealed to the investigator in case of a regulatory audit. Where source documents are required for the continued care of the subject, appropriate copies should be made for storage outside of the site.

13.3 PROTOCOL DEVIATIONS

A Protocol Deviation is any noncompliance with the clinical trial protocol or with GCP. The noncompliance may be either on the part of the subject, the investigator, or the study site staff. When deviations occur, corrective actions are to be developed by the site and implemented promptly.

These practices are consistent with ICH E6:

- 4.5 Compliance with Protocol, sections 4.5.1, 4.5.2, and 4.5.3
- 5.1 Quality Assurance and Quality Control, section 5.1.1
- 5.20 Noncompliance, sections 5.20.1, and 5.20.2.

Protocol Deviations will be categorized as either Major or Minor and will be defined in the study-specific Protocol Deviation Plan.

Major Protocol Deviations are departures from the approved protocol relating to the conduct of the study which may significantly impact the completeness, accuracy, and/or reliability of the study data or that may significantly affect the rights, safety, and/or wellbeing of study participants. Examples of Major Protocol Deviations include, but are not limited to:

- Failure to obtain informed consent (i.e., no evidence of informed consent)
- Enrolling subjects in violation of key eligibility criteria designed to ensure a specific subject population
- A device dispensing or related error that could have affected the safety of the subject
- Failure to collect data necessary to interpret the primary endpoint(s), as this may compromise the scientific value of the trial.

Major Protocol Deviations may result in data that are not deemed evaluable for the *per protocol* analysis and/or may require that subjects are discontinued from the study.

Note: Observations categorized as Major may include those situations where there is a pattern of deviation, numerous Minor observations, or other significant deviation.

Minor Protocol Deviations are departures from the approved protocol relating to the conduct of a study that does not affect the rights, safety, and/or wellbeing of study participants or the study outcomes or data quality. Examples of Minor Protocol Deviations include, but are not limited to:

- A protocol visit date outside of a visit window
- An isolated case of a missed or incomplete study procedure
- An isolated incident of a missed or incomplete study evaluation

Minor Protocol Deviations would not generally preclude subject data from the *per protocol* analysis population. Observations categorized as Minor may become Major if not corrected.

All deviations will be logged and tracked by the site and CRO. Periodic review of Protocol Deviations will serve an indicator of site performance.

Per 21 CFR 812.150(a)(4), it is the responsibility of the site to use continuous vigilance to identify and report deviations promptly (within 5 working days) to the study CRO and/or Sponsor. All deviations must be addressed in study source documents. Notification of Protocol Deviations must be sent to the local IRB per their guidelines. The site investigator/study staff is responsible for knowing and adhering to their IRB requirements.

13.4 PUBLICATION AND DATA SHARING POLICY

In compliance with The International Committee of Medical Journal Editors (ICMJE) clinical trials registration policy and Section 801 of the Food and Drug Administration Amendments Act of 2007, this study will be registered by the Sponsor in ClinicalTrials.gov, a public trials registry which is sponsored by the National Library of Medicine.

Notwithstanding the Sponsor's requirements for registration and data sharing in ClinicalTrials.gov, any formal presentation or publication of data collected as a direct or indirect result of this trial will be considered as a joint publication by the investigator(s) and the Sponsor. In the case of multicenter studies, it is mandatory that the first publication be made based on the totality of data obtained from all centers, analyzed as stipulated in the protocol, and presented and interpreted as documented in the final Clinical Study Report. The resulting publication will name investigators according to the policy of the chosen journal. Where it is not permitted for all investigators to be included as authors, the publication will name all investigators within the publication.

Individual investigators may publish data arising from their own subjects. The investigator will provide the Sponsor with copies of written publications (including abstracts and posters) at least 60 days in advance of submission. This review is to permit the Sponsor to review the communication for accuracy (thus avoiding potential discrepancies with submissions to regulatory authorities), to verify that confidential information is not inadvertently divulged (including patent protection), to allow adequate input or supplementary information that may not have been available to the investigator, and to allow establishment of co-authorship.

Investigators participating in multicenter studies must agree not to engage in presentations based on data gathered individually or by a subgroup of centers before publication of the first main publication unless this has been agreed otherwise by all other investigators and the Sponsor. However, in the event that no publication of the overall results has been submitted after approval of the Clinical Study Report, investigators may publish results of one or more center's subjects to the same review as outlined above. The Sponsor will circulate proposed multicenter publications to all investigators for review.

Data will be reviewed by all participating investigators prior to publication. The study Sponsor will have 90 days to review all definitive publications, such as manuscripts and book chapters, and a minimum of 30 days to review all abstracts.

14 FINANCIAL DISCLOSURE AND CONFLICT OF INTEREST POLICY

A separate financial disclosure agreement will be made between each investigator and Alkahest, Inc. or its authorized representative before the study device is shipped. Each investigator will notify Alkahest, Inc. or its authorized representative of any relevant changes during the conduct of the study and for 1 year after the study has been completed. Alkahest and the study CRO will evaluate any disclosed conflicts of interest and will establish a mechanism for their management.

15 SCHEDULE OF EVENTS

15.1 SCHEDULE OF STUDY EVENTS

SECTION 15.1.1 SCREENING AND RUN-IN

Procedures		Visits 1.1 – 1.6: Run-In						
Visit Number	Visit 1: Screening ¹	V1.1	V1.2	V1.3	V1.4	V1.5	V1.6	
Study Week	Week -6 to -2			Week -2 to -1				
Study Day(s)	Days -42 to -14			Days -14 to -1				
Informed consent	X							
Demographics	X							
Medical history	X							
Physical examination	X							
12-lead ECG	X							
Height	X							
Weight	X	X	X	X	X	X	X	
Targeted physical exam		X	X	X	X	X	X	
Vital signs ²	X	X	X	X	X	X	X	
Laboratory tests ³	X		X ⁴				X ⁴	
Serum pregnancy test (WOCBP only)	X						X (V1.5 or V1.6)	
Hemodialysis @ maximum flow rate of 250 mL/min		X	X	X	X	X	X	
MoCA, PHQ-9 ⁵	X							
Cogstate test battery ⁶		Complete a total of two familiarization assessments prior to V2.1						
Blood sample for b2M ⁷	X (local lab)					X		
Blood sample for plasma proteomics ⁷						X		
Adverse events and concomitant medications	X	X	X	X	X	X	X	

1. The Screening Visit may be split to allow for sufficient time to complete all procedures. AEs and concomitant medications should be reviewed during split visits, as applicable.

2. For additional information, see [Section 7.1.1.2.2](#).

3. For additional information, see [Section 7.1.1.1.5](#) and [Section 15.2 Schedule of Laboratory Tests](#).

4. Laboratory testing for BUN, creatinine, and aPTT only. Samples should be taken prior to HD and again mid-way through HD (~2 hrs into treatment). Samples for aPTT may be taken anytime blood clots are suspected in the circuit or at the discretion of the investigator.

5. For additional information, see [Section 7.1.1.1.7](#) and [Section 7.1.1.1.8](#).

6. For additional information, see [Section 7.1.1.3.3](#).

7. For additional information, see [Section 7.1.1.1.9](#). The V1 b2M sample is to be assayed at a local lab for screening purposes. This sample should be collected prior to HD or on a non-dialysis day.

8. For additional information, see [Section 7.2.2.1](#) and [Section 15.2 Schedule of Laboratory Tests](#).

SECTION 15.1.2 TREATMENT PERIOD 1 (VISIT 2/MONTH 1)

Procedures												
Visit	Visit 2: Treatment Period 1											
Visit Number	2.1	2.2	2.3	2.4	2.5	2.6	2.7	2.8	2.9	2.10	2.11	2.12
Study Week	Week 1			Week 2			Week 3			Week 4		
Study Day (± 1 day)	Day 1	Day 3	Day 5	Day 8	Day 10	Day 12	Day 15	Day 17	Day 19	Day 22	Day 24	Day 26
Verify eligibility ¹	X											
Randomization ²	X											
HD (250 mL/min for ~4 h)	X	X	X	X	X	X	X	X	X	X	X	X
AKST1210 S-15 or control	X	X	X	X	X	X	X	X	X	X	X	X
Vitals signs ³	X	X	X	X	X	X	X	X	X	X	X	X
Targeted physical exam	X	X	X	X	X	X	X	X	X	X	X	X
Weight	X	X	X	X	X	X	X	X	X	X	X	X
Laboratory tests (local lab) ⁴	X	X			X		X	X				X
Cogstate test battery, FACIT, PSQI, SF-36	X											
Blood samples for b2M ⁵												X
Blood samples for plasma proteomics ⁶												X
Assessment of fluid status ⁷	X	X	X	X	X	X	X	X	X	X	X	X
Adverse events and concomitant medications	X	X	X	X	X	X	X	X	X	X	X	X
Monitor tolerability per Appendix 17.1	X	X	X	X	X	X	X	X	X	X	X	X ⁸

1. Assess tolerability of Run-in period prior to randomization (see [Section 5.2](#)).
2. Refer to the Device Procedures Manual for guidance.
3. Vital signs to be collected at multiple timepoints, see [Section 7.1.1.2.2](#).
4. For additional information, see [Section 7.1.1.2.5](#) and [Section 15.2 Schedule of Laboratory Tests](#).
5. For additional information, see [Section 7.1.1.1.9](#) and [Section 15.2 Schedule of Laboratory Tests](#).
6. For additional information, see [Section 7.2.2.1](#) and [Section 15.2 Schedule of Laboratory Tests](#).
7. For additional information, see [Section 7.1.1.2.3](#).
8. Post HD, if subject has not already been discontinued, evaluate for escalation to S-25 per [Appendix 17.1](#).

SECTION 15.1.3 TREATMENT PERIOD 2 (VISIT 3/MONTH 2)

Procedures												
Visit	Visit 3: Treatment Period 2											
Visit Number	3.1	3.2	3.3	3.4	3.5	3.6	3.7	3.8	3.9	3.10	3.11	3.12
Study Week	Week 5			Week 6			Week 7			Week 8		
Study Day (± 1 day)	29	31	33	36	38	40	43	45	47	50	52	54
HD (250 mL/min for ~ 4 h)	X	X	X	X	X	X	X	X	X	X	X	X
AKST1210 S-25 or control	X	X	X	X	X	X	X	X	X	X	X	X
Vitals signs ¹	X	X	X	X	X	X	X	X	X	X	X	X
Targeted physical exam	X	X	X	X	X	X	X	X	X	X	X	X
Weight	X	X	X	X	X	X	X	X	X	X	X	X
Laboratory tests (local lab) ²	X	X			X		X	X				X
Cogstate test battery, FACIT, PSQI, SF-36	X											
Blood samples for b2M ³												X
Blood samples for plasma proteomics ⁴												X
Assessment of fluid status ⁵	X	X	X	X	X	X	X	X	X	X	X	X
Adverse events and concomitant medications	X	X	X	X	X	X	X	X	X	X	X	X
Monitor for de-escalation or discontinuation per Appendix 17.1	X	X	X	X	X	X	X	X	X	X	X	X ⁶

1. Vital signs to be collected at multiple timepoints, see [Section 7.1.1.2.2](#).

2. For additional information, see [Section 7.1.1.2.5](#) and [Section 15.2 Schedule of Laboratory Tests](#).

3. For additional information, see [Section 7.1.1.1.9](#) and [Section 15.2 Schedule of Laboratory Tests](#).

4. For additional information, see [Section 7.2.2.1](#) and [Section 15.2 Schedule of Laboratory Tests](#).

5. For additional information, see [Section 7.1.1.2.3](#).

6. Post HD, if subject has not already been de-escalated or discontinued, evaluate for escalation to S-35 per [Appendix 17.1](#).

SECTION 15.1.4 TREATMENT PERIOD 3 (VISIT 4/MONTH 3)

Procedures												End of Tx
Visit	Visit 4: Treatment Period 3											End of Tx
Visit Number	4.1	4.2	4.3	4.4	4.5	4.6	4.7	4.8	4.9	4.10	4.11	4.12
Study Week	Week 9			Week 10			Week 11			Week 12		
Study Day (± 1 day)	57	59	61	64	66	68	71	73	75	78	80	82
HD (250 mL/min for ~ 4 h)	X	X	X	X	X	X	X	X	X	X	X	
AKST1210 S-35 or control	X	X	X	X	X	X	X	X	X	X	X	
Vitals signs ¹	X	X	X	X	X	X	X	X	X	X	X	
Targeted physical exam	X	X	X	X	X	X	X	X	X	X	X	
Weight	X	X	X	X	X	X	X	X	X	X	X	
Laboratory tests ²	X	X			X		X	X		X		
Cogstate test battery, FACIT, PSQI, SF-36	X											
Blood samples for b2M ³												X
Blood samples for plasma proteomics ⁴												X
Assessment of fluid status ⁵	X	X	X	X	X	X	X	X	X	X	X	
Adverse events and concomitant medications	X	X	X	X	X	X	X	X	X	X	X	
Monitor for de-escalation or discontinuation per Appendix 17.1	X	X	X	X	X	X	X	X	X	X	X	

Refer to
Section
15.1.5

1. Vital signs to be collected at multiple timepoints, see [Section 7.1.1.2.2](#).

2. For additional information, see [Section 7.1.1.2.5](#) and [Section 15.2 Schedule of Laboratory Tests](#).

3. For additional information, see [Section 7.1.1.1.9](#) and [Section 15.2 Schedule of Laboratory Tests](#).

4. For additional information, see [Section 7.2.2.1](#) and [Section 15.2 Schedule of Laboratory Tests](#).

5. For additional information, see [Section 7.1.1.2.3](#).

SECTION 15.1.5 END OF TREATMENT AND END OF STUDY VISITS

Procedures	Visit	Visit 5: End of Treatment	Visit 6: End of Study (EOS)
Study Week		Week 12 (continued)	Week 14
Study Day		Day 82 ± 1	Day 96 ± 3
Targeted physical examination		X	X
Weight		X	X
12-lead ECG			X
Vital signs ¹		X	X
Laboratory tests ²		X ²	X ³
Serum pregnancy test (WOCBP only)			X
HD		250 mL/min flow rate for ~4h	X (flow rate per standard of care)
AKST1210 or Control		X	
MoCA, PHQ-9			X
Cogstate test battery, FACIT, PSQI, SF-36		X	X
Blood sample for b2M ⁴			X
Blood sample for plasma proteomics ⁵			X
Assessment of fluid status ⁶		X	X
Adverse events and concomitant medications		X	X

1. For additional information, see [Section 7.1.1.2.2](#).

2. Refer to [Section 15.2 Schedule of Laboratory Tests](#).

3. Refer to [Section 7.1.1.2.5](#) and [Section 15.2 Schedule of Laboratory Tests](#).

4. For additional information, see [Section 7.1.1.1.9](#) and [Section 15.2 Schedule of Laboratory Tests](#).

5. For additional information, see [Section 7.2.2.1](#) and [Section 15.2 Schedule of Laboratory Tests](#).

6. For additional information, see [Section 7.1.1.2.3](#).

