6.1.5 COLUMN SIZE ESCALATION AND ADMINISTRATION

The initial AKST1210 size used during Weeks 1 to 4 (Treatment Period 1) will be the 150 mL column

(AKST1210 S-15). Following evaluation for IDH Rate and anemia (see [Appendix 17.1](#)), subjects may be escalated to the 250 mL column (AKST1210 S-25) for Weeks 5 to 8, followed by the 350 mL column (AKST1210 S-35) for Weeks 9 to 12. The subject, investigator, and outcomes assessor must remain blinded to treatment assignment at all times. Careful attention should be given to ensure that all subjects, regardless of treatment assignment, undergo the same evaluations for escalation, de-escalation, and discontinuation.

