17 APPENDICES

APPENDIX 17.1 ESCALATION, DE-ESCALATION, AND DISCONTINUATION RULES FOR TREATMENT WITH AKST1210 OR CONTROL

The following definitions are relevant to evaluating whether to escalate, de-escalate, or discontinue a subject:

- **Intradialytic hypotension/hypotensive event (IDH):** A decrease in SBP \geq 20 mm Hg or a decrease in MAP \geq 10 mm Hg associated with symptoms that include: abdominal discomfort; yawning; sighing; nausea; vomiting; muscle cramps; restlessness; dizziness or fainting; and anxiety ([K/DOQI Workgroup 2005](#)).
- **Expected IDH Rate:** The expected number of occurrences of IDH per 4-week treatment period used to assess escalation, de-escalation, and discontinuation. Expected IDH is derived from a subject's Historical IDH Rate (see table below).
- **Historical IDH Rate:** The number of occurrences of IDH as documented in a subject's medical record during a recent, consecutive 8-week interval prior to randomization. This 8-week period may include the 2-week Run-in. Subjects with 5 or more IDH events during this 8-week interval will be excluded.

The table below provides the corresponding Expected IDH Rate based on the Historical IDH Rate and summarizes the rules for escalation, de-escalation, or discontinuation based on the number of occurrences of IDH.

Historical IDH Rate over 8 weeks	Expected IDH Rate over 4 weeks	Escalation Rule	De-escalation or Discontinuation Rule
0	0	1 or less	2 in 4 weeks
1	1	2 or less	3 in 4 weeks
2	1		
3	2	3 or less	4 in 4 weeks
4	2		

Escalation Rules: A subject may be escalated to the next larger column size if they experience no more than 1 IDH event above their Expected IDH Rate in a 4-week treatment period and has an Hgb level \geq 9 g/dL.

De-escalation Rules: A subject should be de-escalated to a previously tolerated column size if at any time during a 4-week treatment period they experience 2 or more IDH events above the Expected IDH Rate and/or has a Hgb level $<$ 9 g/dL despite optimized ESA treatment.

Discontinuation Rules: A subject should be discontinued if they experience 2 or more IDH events above their Expected IDH Rate in a 4-week treatment period after de-escalation to the lowest column size (AKST1210 S-15) and/or has an Hgb level $<$ 9 g/dL despite optimized ESA treatment after de-escalation to the lowest column size (AKST1210 S-15). Subjects may also be discontinued at any time at the discretion of the investigator.

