5.1 General Considerations

This section presents the statistical approaches that are anticipated for the analysis of the study data. These approaches may at times require modifications due to unanticipated features of the data. Deviations from analyses summarized in this document will be noted in the CSR.

All statistical analyses will be performed using SAS® Version 9.4 or higher, unless otherwise noted. Data will be summarized using descriptive statistics, unless otherwise noted. Number of subjects (n) with non-missing values mean, median, standard deviation, minimum, and maximum will be summarized for continuous (quantitative) variables. Categorical (qualitative) variables will be summarized using frequencies and percentages of subjects who are in a particular category or each possible value. In general, the denominator for the percentage calculation will be based upon the total number of subjects in the study population for each treatment group, unless otherwise specified. The denominator for by-visit displays will be the number of subjects in the relevant study population with non-missing data at each visit. Presentations will be by treatment group (AKST1210 and Control) and Total, unless otherwise noted.

The minimum and maximum will be reported with the same degree of precision (i.e., the same number of decimal places) as the observed data. Measures of location (mean and median) will be reported to 1 degree precision more than the observed data and measures of spread (SD) will be reported to 2 degrees of precision more than the observed data.

Percentages will be presented to 1 decimal place, unless otherwise specified. Percentages will not be displayed when the numerator for a cell is 0.

Unless otherwise indicated, all statistical tests will be conducted at 0.05 significance level using 2-tailed tests, and P values will be reported. Corresponding 95% CIs will be presented for statistical tests.

In general, all summary tables will be supported by a relevant subject data listing including all subjects who are randomized. The listings will include all data collected, and will be sorted by subject ID, and actual visit date, as applicable, unless otherwise noted. The listing will also include the column size for each of the three treatment periods as applicable.

Study day 1 is the first day of HD treatment with AKST1210 or control. Study day is the day relative to the study day 1.

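### For a subject held on S-15 who qualifies on Day 54, Protocol Appendix 17.1 leads to S-25 in Period 3, while 15.1.3 footnote 6 and the 15.1.4 column row name only S-35

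*Protocol*

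**What the plan says.** Appendix 17.1 of the protocol defines escalation as a single step: "A subject may be escalated to the next larger column size if they experience no more than 1 IDH event above their Expected IDH Rate", with Hgb of at least 9 g/dL as the other condition. It does not exclude subjects who were held back or de-escalated earlier.

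The schedule of events names sizes. At the end of Period 1, 15.1.2 footnote 8 reads: "Post HD, if subject has not already been discontinued, evaluate for escalation to S-25". At the end of Period 2, 15.1.3 footnote 6 reads: "Post HD, if subject has not already been de-escalated or discontinued, evaluate for escalation to S-35". Both footnotes refer to Appendix 17.1. The column rows are "AKST1210 S-25 or control" for Period 2 and "AKST1210 S-35 or control" for Period 3, with no entry for a subject on another size.

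Protocol 6.1.5 describes only the uninterrupted sequence: "subjects may be escalated to the 250 mL column (AKST1210 S-25) for Weeks 5 to 8, followed by the 350 mL column".

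SAP 4.7 provides for de-escalation, escalation or discontinuation to be evaluated on Day 54, without the footnote's restriction on de-escalated subjects.

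**The concern.** The footnote adds two things that the Appendix lacks: a fixed target size (S-35), and the exclusion of subjects already de-escalated. The target fits a subject who spent Period 2 on S-25. It does not fit one who spent Period 2 on S-15, for whom the next size up is S-25. No text says which page governs.

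At stake is the device size given in Weeks 9 to 12 to a subject previously held back on a tolerability criterion, and hence who belongs to the S-35 group. Tolerability of each size escalation is a secondary endpoint. The SAP summarizes tolerability (5.7.2), IDH (5.7.3), worsening anemia (5.7.5) and treatment duration (5.7.8) by column size, and its third b2M hypothesis (5.7.7) uses column size as a factor. With about 10 active subjects, one subject is about 10% of a by-size cell.

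**Working it through.** **1. Appendix 17.1 table.** Taking Expected = Historical/2 rounded up, escalation at Expected + 1 or fewer, and de-escalation or discontinuation at Expected + 2 or more:

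| Historical (8 wk) | Expected (4 wk) | Escalate at or below | De-escalate or discontinue at |
|---|---|---|---|
| 0 | 0 | 1 | 2 |
| 1 | 1 | 2 | 3 |
| 2 | 1 | 2 | 3 |
| 3 | 2 | 3 | 4 |
| 4 | 2 | 3 | 4 |

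All five rows match the protocol, so the IDH thresholds agree among themselves and leave no gap between escalating and stepping down.

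**2. Can a subject be held on S-15 into Period 2?** Yes, through Hgb. A value below 9 g/dL blocks escalation by itself, but de-escalation requires that it stay low once ESA has been optimized. Discontinuation for Hgb is written only for subjects already de-escalated to S-15. A subject with low Hgb on Day 26 whose ESA is still being adjusted therefore meets neither rule. Escalation is also worded as permissive, so investigator discretion is a second route.

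**3. Period 3 column by state at the end of Period 2.**

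| State on Day 54 | Appendix 17.1 | Footnote 6, literal |
|---|---|---|
| (a) On S-25, criteria met | S-35 | S-35 |
| (b) Held on S-15, criteria met | S-25 | S-35 |
| (c) Held on S-15, criteria not met | no escalation | no escalation |
| (d) De-escalated to S-15 for IDH | no escalation | not evaluated |
| (e) De-escalated to S-15 for Hgb only, Hgb recovered, IDH within limit | S-25 | not evaluated |

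The outcome differs in (b) and (e). In (d) it is the same, because the period's IDH count already exceeds Expected + 1. That would change only if the count restarted after de-escalation, which the Appendix does not say. Only (b) alters who receives S-35.

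**4. Size of the step (Protocol Table 2, extracorporeal volume).** S-15 to S-25: 105 − 65 = 40 mL. S-15 to S-35: 177 − 65 = 112 mL.

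**5. Number affected.** The documents give no frequency for path (b), so a share p of 0% to 30% is assumed. With 10 active subjects (the planned evaluable number per arm) and all others reaching S-35, the expected S-35 group is 10(1 − p) under the Appendix and 10 under the literal footnote. The chance of at least one such subject is 1 − (1 − p)^10.

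| p (assumed) | S-35 group, Appendix | S-35 group, footnote | Chance of at least one |
|---|---|---|---|
| 0% | 10 | 10 | 0% |
| 5% | 9.5 | 10 | 40% |
| 10% | 9 | 10 | 65% |
| 20% | 8 | 10 | 89% |
| 30% | 7 | 10 | 97% |

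**The case against.** The strongest reply is that footnote 6 defers to Appendix 17.1, as do the design section and 6.1.5. The Appendix allows one step, 6.1.5 puts S-35 after S-25, and nothing expressly authorizes skipping a size. The single-size rows can be taken as nominal labels, since they also omit de-escalated subjects, whom the protocol plainly allows for. This carries weight: many sites may resolve the conflict through the Appendix, and a reader who infers that sites will in fact give different columns goes beyond the text. But the cross-reference does not remove the named target. A held subject can meet the Appendix criteria and still be the subject of an evaluation for S-35.

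The held path is also narrow. The IDH thresholds leave no middle zone, and SAP 4.7 lists only escalation or discontinuation for Day 26. That stands, and leaves Hgb and discretion as the routes.

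The de-escalation conflict is narrower still. As the extracted laboratory schedule reads (its columns may be broken), the scheduled Hgb days around Period 2 are Days 29, 43 and 57. A subject de-escalated on the Day 43 value would then have no scheduled Hgb to show recovery by Day 54.

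Two stronger readings do not hold. A reader might infer that all by-size results depend on the page followed; Period 1 and Period 2 column assignments do not. A reader might also infer that the SAP codes each period by one size, so that events triggering a de-escalation move to the smaller column. The sentence suggesting this, "The listing will also include the column size for each of the three treatment periods as applicable", concerns subject data listings. The SAP does not state how events are attributed after a mid-period change, and no last-size rule appears.

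**Conclusion.** The protocol is inconsistent as written for one reachable path: a subject held on S-15 through Period 2 who meets the criteria on Day 54. The literal texts give S-25 or S-35, a difference between 40 mL and 112 mL of added extracorporeal volume. The bar on re-evaluating de-escalated subjects is a second, smaller inconsistency. It matters for Hgb-only de-escalation with recovery and never changes S-35 membership.

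The effect is confined to Period 3 column assignment and what Period 3 adds to the by-size summaries. It amounts to 0 to 3 of 10 active subjects, given the assumed 0% to 30% share and every other subject reaching S-35. If nobody takes the held path, the S-35 group is unchanged. Which clinical rule is right is not judged here.

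A secondary point for the SAP is that Table 1 attaches S-15, S-25 and S-35 to V2.11, V3.11 and V4.11 as a sampling plan, and the text does not say whether by-size analyses use that nominal size or the actual one. For a held or de-escalated subject the two differ.

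**What to change.** Reconcile Appendix 17.1, 15.1.3 footnote 6, the Period 2 and Period 3 column rows, and 6.1.5, so that one rule covers subjects held on S-15 and subjects de-escalated in Period 2. The sponsor decides which rule. The same text should say whether a de-escalated subject may be evaluated again and whether the IDH count restarts, and SAP 4.7 should match.

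In the SAP, state that the by-size summaries and the b2M size model use the column in use at the session concerned, not the nominal size in Table 1. Flag Hgb values and AEs after a size change as possible carry-over; do not credit them automatically to the newer size, because a fall in Hgb that began on the larger column may persist after de-escalation.

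The cost is a protocol clarification and a few SAP sentences. Protocol 6.2 already requires dispensing records with date and column size, so no new data are needed. Those records are unblinding and must stay restricted until the blind is broken.
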